## **13.2** Definitions of Analysis Sets

- The Full Analysis Set (FAS) population will serve as the population for the analysis of primary efficacy endpoint TIL density in this study. The FAS population consists of all participants within each cohort who have received a preoperative dose of VB-111/placebo and had a surgery.
- The intention to treat (ITT) population is defined as all randomized participants. The ITT population will be used for secondary efficacy endpoints (PFS6, OS).
- The All Participants as Treated (APaT) population will be used for the analysis of safety data in this study. The APaT population consists of all allocated participants who received at least one dose of study treatment. At least one laboratory or vital sign measurement obtained subsequent to at least one dose of study treatment is required for inclusion in the analysis of each specific parameter. To assess change from baseline, a baseline measurement is also required.

A randomized, placebo controlled phase II, surgical trial to evaluate early immunologic pharmacodynamic parameters for the viral cancer therapy ofranergene obadenovec (VB-111) in patients with surgically accessible recurrent/progressive glioblastoma Version 3.0 February 18, 2021

## 13.3 Sample Size Consideration

This is a randomized, controlled, blinded, phase II, surgical trial to evaluate early immunologic pharmacodynamic parameters for the viral cancer therapy VB-111 in participants with surgically accessible recurrent/progressive glioblastoma (rGBM). Participants will be randomly assigned to group A or B or C with a 1:1: 1 randomization ratio prior to surgery. The primary hypothesis is that VB-111 can generate effective anti-tumor immune responses in the form of a statistically significant increase in TIL density comparing Group A (neoadjuvant/adjuvant) vs combined control group (Group B+C).

Based on our preliminary data, the mean of TIL density is estimated to be 0.4 (T cells per nucleated cell) (SD=0.5) in the combined control group (Group B and C). Comparing Group A vs Group B+C at an alpha level of 0.05 (1-sided) using a stratified two-sample t-test, a sample size of 30 in the combined Group (B+C), and 15 in Group A (Total of 45 evaluable) allows for the detection of a standard difference in TIL density of 0.8 or larger with 84% power. Effect size is defined as Cohen's D, the difference of two population means, divided by the pooled standard deviation. [63]

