A Phase 3, multisite, international, randomized, open-label, controlled trial in participants with rGBM after first or second progression (GLOBE) was performed to confirm earlier findings. However, the sequencing of VB-111 and bevacizumab was unlike the initial Phase 2 study. In this study, bevacizumab was given together with VB-111 instead of upon progression. Participants were randomized 1:1 to receive VB-111 at 10^13 VPs q8w in combination with bevacizumab 10mg/kg q2w (combination arm) or monotherapy with bevacizumab 10mg/kg q2w (control arm). The primary endpoint of OS and secondary endpoints of objective response rate (ORR) by Response Assessment in Neuro-Oncology (RANO) criteria, Progression Free Survival (PFS) and safety were investigated in two hundred fifty-six participants enrolled in 57 sites. In the combination vs the control arm, median exposure to VB-111 was 4 months. Median OS was 6.8 vs 7.9 months (HR 1.2 [95% CI 0.91-1.59, p=NS]). ORR was 27.3% vs 21.9% (p=0.26), respectively. VB-111 in combination with bevacizumab failed to increase OS. We believe that lack of VB-111 monotherapy priming may explain the difference from the favorable Phase 2 outcome.

To further explore the role of priming, this study will explore the effects of single-dose neoadjuvant VB-111, followed by adjuvant treatment. The primary endpoint will be to evaluate whether neoadjuvant VB-111 increases the density of tumor infiltrating T cells (TIL) within recurrent glioblastoma. To assess the baseline TIL density, we extracted genomic DNA from 62 GBM samples (newly diagnosed and recurrent). The samples were subjected to next generation T cell receptor sequencing at Adaptive Biotechnologies (Seattle, WA). The average TIL density was 0.50 +/- 0.68 % T cells/nucleated cell (obtained from fresh-frozen tumor tissue). No statistically significant differences in TIL density were found between recurrent and newly diagnosed glioblastoma samples.

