# 5.6 Participant Evaluability

If pre-operative VB-111/placebo is not able to be given to a participant or a participant did not undergo the scheduled surgical resection for any reason, then the participant will be unevaluable for the primary efficacy analysis. Additional patients will be recruited to the trail until 15 evaluable patients in each arm.

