## **13.1.1 Efficacy Endpoints**

Tumor infiltrating T cell (TIL) density is defined as the number of T lymphocytes per nucleated cell, and calculated by detailed sequencing of recombined T cell receptor sequences obtained from the tumor specimen gDNA.

PFS6 is defined as the percentage of participants with progression-free survival at 6 months from surgery as defined by RANO.

OS is defined as the time from randomization until death from any cause. Participants will be followed for survival status after progression or discontinuation of the study drug for other reasons.

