## 13.4 Efficacy Analysis

A two-sample t-test with tumor size stratification will be used to test the difference of tumor infiltrating T cell density between the two groups (Group A vs combined Group B+C). Data distribution will be examined prior to analysis. Data transformations will be performed as deemed appropriate.

For the secondary endpoint of PFS6, historical comparison data are available from a pooled analysis of Phase II experience in recurrent Grade IV gliomas who have undergone surgery either just prior to starting treatment or as part of the protocol, which documented a PFS6 rate of 10%. Group comparisons (Group A vs C; Group B vs C; Group A+B vs C) will be conducted using the exact binomial test with Bonferroni adjustment to compare PFS6 rate at one sided alpha of 5%.

For OS, analyses will be conducted using historical comparison data which are available from a pooled analysis of Phase II experience in recurrent Grade IV gliomas who have undergone surgery either just prior to starting treatment or as part of. Kaplan-Meier (KM) curves and median estimates from the KM curves will be provided as appropriate. Participants without efficacy evaluation data or without survival data will be censored at Day 1. For evaluation of the expansion of TCR clones, a two-sample T-test with Bonferroni adjustment will be used to compare the increase number of expanded TCR clones after VB-111 in Group A+B vs Group C.

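### Section 13.3 claims 84% power at d = 0.8, but its own design (15 versus 30, one-sided 0.05) gives 80%

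*Combined protocol and SAP*

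**What the plan says.** Section 13.3 (Sample Size Consideration) sets out the power calculation for the primary efficacy endpoint, TIL density in Group A against Groups B and C combined. The comparison is made "at an alpha level of 0.05 (1-sided) using a stratified two-sample t-test", with "a sample size of 30 in the combined Group (B+C), and 15 in Group A (Total of 45 evaluable"). The conclusion is that this design "allows for the detection of a standard difference in TIL density of 0.8 or larger with 84% power". The effect size is defined there as Cohen's d, with the pooled standard deviation as the divisor.

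The rest of the plan agrees with these group sizes. Section 5.1 assigns fifteen participants to each of three groups at 1:1:1. Section 5.6 replaces unevaluable participants: "Additional patients will be recruited to the trail until 15 evaluable patients in each arm". Section 13.4 repeats the test: "A two-sample t-test with tumor size stratification will be used to test the difference of tumor infiltrating T cell density between the two groups".

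For the planning values, Section 13.3 cites preliminary data: "the mean of TIL density is estimated to be 0.4 (T cells per nucleated cell) (SD=0.5"). The only preliminary TIL data shown are in Section 2.2.2, from 62 newly diagnosed and recurrent samples: "The average TIL density was 0.50 +/- 0.68 % T cells/nucleated cell".

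**The concern.** The group sizes, alpha, sidedness, test and standardized effect are all printed, so the power can be checked directly. For a fixed total, a 1:2 comparison has less power than an equal split, and 84% looked too high for 15 against 30.

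This is the only power statement for the primary efficacy endpoint. Readers will use it to judge what a null result means, and an overstated figure makes such a result look more informative than it is.

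A lesser matter concerns the planning values. The mean of 0.4 and SD of 0.5 are not traced to the 0.50 and 0.68 in Section 2.2.2, where the spread is not labelled as an SD. Section 2.2.2 also reports TIL density in percent, whereas Section 13.1.1 says it "is defined as the number of T lymphocytes per nucleated cell" and Section 13.3 likewise has no percent sign. Neither point affects the power, because d has no unit.

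**Working it through.** **Inputs.** From Section 13.3: n1 = 15, n2 = 30, d = 0.8, one-sided alpha 0.05, two-sample t-test. No dropout allowance applies, because 45 is the evaluable number and Section 5.6 replaces unevaluable participants.

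**Power at the stated design**

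1. Noncentrality = d × √(n1·n2/(n1+n2)) = 0.8 × √(15 × 30/45) = 0.8 × √10 = 2.530.
2. Degrees of freedom = 15 + 30 − 2 = 43; one-sided 5% critical value 1.681.
3. Power = P(noncentral t with 43 df and noncentrality 2.530 exceeds 1.681) = 0.8009.

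The stated 84% is not reproduced. Three checks on the result:

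| Check | Power |
|---|---|
| One df spent on the tumor-size stratum (df = 42) | 0.8006 |
| Normal approximation, Φ(2.530 − 1.645) | 0.8119 |
| Simulation, 400,000 trials | 0.8014 |

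**Other readings of alpha or test.** Two-sided 0.05, or one-sided 0.025, gives 69.6%. A rank test with asymptotic relative efficiency 0.955 gives 78.4%. All move further from 84%.

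**What would give 84%**

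| Change from the stated design | Power |
|---|---|
| 22 versus 23, d = 0.8 (noncentrality 0.8 × √(22 × 23/45) = 2.683) | 84.0% |
| 15 versus 45, d = 0.8 | 84.3% |
| 17 versus 34, d = 0.8 | 84.4% |
| 15 versus 30, d = 0.848 | 84.0% |
| 15 versus 30, d = 0.85 | 84.1% |
| 15 versus 30, d = 0.8, stratum explains 10% of variance (df = 42) | 83.6% |
| 15 versus 30, d = 0.8, stratum explains 12% of variance (df = 42) | 84.3% |

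For the stratum rows, the effective standardized difference is 0.8/√(1 − R²). Exactly 84% needs R² = 0.111, since 0.8/√0.889 = 0.848.

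**Size of the discrepancy.** Power: 84 − 80.1 = 3.9 percentage points. Type II error at d = 0.8: 100 − 80.1 = 19.9%, against the implied 100 − 84 = 16%.

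**The case against.** Three arguments can be made for the printed figure.

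- **Rounding of d.** The effect is given to one decimal. Values from 0.842 to just under 0.85 print as 0.8 and give power that rounds to 84% with 15 versus 30. This is arithmetically possible, and the error might then lie in the printed d. But the text sets 0.8 as the lower limit of the detectable range, so the claim has to hold at 0.8. With an SD of 0.5, d = 0.8 is also a difference of exactly 0.8 × 0.5 = 0.4, equal to the control mean, which suggests that 0.8 was meant exactly.
- **Stratification.** The test is described as stratified by tumor size, and the 80.1% assumes that the stratum explains none of the variance in TIL density. A share of about 11% would bring the power to 84%. The plan neither states nor supports such a gain, and it defines d with the pooled SD. If the gain was assumed, the assumption is missing.
- **Unequal SDs.** A Welch test with a Group A SD about 0.7 times that of controls gives 83.9% in simulation. The plan assumes nothing of the kind.

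It is also fair to say that the consequence is modest. About 80% is a conventional level of power, and no enrollment or analysis decision changes. Several different inputs lead to 84%, so the match with an equal split does not establish the cause. The missing percent sign is a labelling slip, and planning values that differ from the 62-sample summary may come from a subset or from other data. These points limit the weight of the finding, but they do not make the printed sentence correct.

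**Conclusion.** The concern holds. For the design printed in Section 13.3, power at d = 0.8 is 80.1%, not 84%. The result rests on the printed inputs, normally distributed data with a common SD, and no variance reduction from the tumor-size stratum. Under the same conditions 84% power belongs to d of about 0.85. How the 84% arose cannot be settled from the documents. The design remains defensible at 80%, but the power statement for the primary endpoint needs correcting.

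**What to change.** In Section 13.3, do one of the following:

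- state 80% power for d = 0.8 with 15 versus 30;
- state that 84% power applies to d of about 0.85; or
- if a variance reduction from tumor-size stratification was assumed, say so, give its size (about 11% of TIL variance is needed) and justify it.

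In the same edit, name the source of the mean of 0.4 and SD of 0.5, and use the percent unit consistently in Sections 2.2.2, 13.1.1 and 13.3.

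The cost is a few words of text. Under the first option the stated power falls from 84% to 80%. Sample size, alpha and test are unchanged.

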## 13.4 Efficacy Analysis

A two-sample t-test with tumor size stratification will be used to test the difference of tumor infiltrating T cell density between the two groups (Group A vs combined Group B+C). Data distribution will be examined prior to analysis. Data transformations will be performed as deemed appropriate.

For the secondary endpoint of PFS6, historical comparison data are available from a pooled analysis of Phase II experience in recurrent Grade IV gliomas who have undergone surgery either just prior to starting treatment or as part of the protocol, which documented a PFS6 rate of 10%. Group comparisons (Group A vs C; Group B vs C; Group A+B vs C) will be conducted using the exact binomial test with Bonferroni adjustment to compare PFS6 rate at one sided alpha of 5%.

For OS, analyses will be conducted using historical comparison data which are available from a pooled analysis of Phase II experience in recurrent Grade IV gliomas who have undergone surgery either just prior to starting treatment or as part of. Kaplan-Meier (KM) curves and median estimates from the KM curves will be provided as appropriate. Participants without efficacy evaluation data or without survival data will be censored at Day 1. For evaluation of the expansion of TCR clones, a two-sample T-test with Bonferroni adjustment will be used to compare the increase number of expanded TCR clones after VB-111 in Group A+B vs Group C.

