# **1.3** Secondary Objectives & Hypotheses

**Secondary Objective 1**: To estimate the 6-month progression-free survival (PFS6) in recurrent/progressive GBM participants treated with VB-111 (Group A and Group B) compared to control (Group C), using RANO criteria.

**Hypothesis 1:** We hypothesize that a greater percentage of participants who are treated with VB-111 will not have experienced tumor progression at 6 months after treatment.

**Secondary Objective 2:** To calculate the overall survival of recurrent/progressive GBM participants in each arm.

**Hypothesis 2:** We hypothesize that progressive/recurrent GBM participants treated with VB-111 will live significantly longer than Group C and/or historical controls of this participant population.

**Secondary Objective 3:** To evaluate the influence of VB-111 on peripheral T cell responses, specifically on expanded TCR clones.

**Hypothesis 3:** We hypothesize that specific subsets of TCR clones will expand in response to VB-111.

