## 5.1 Treatment Regimen

Participants will be screened for eligibility up to 14 days prior to randomization. They will be sequentially randomized to one of three groups in a 1:1:1 ratio of the Neoadjuvant/Adjuvant arm (Group A), Adjuvant arm (Group B), and Control arm (Group C).

Group A (Neoadjuvant/adjuvant): Fifteen participants will receive VB-111 at 1x10^13 VPs intravenously 21±7 days prior to surgery. Tumor samples will be obtained at time of surgery, and tissue (fresh, frozen and FFPE) will be processed to achieve primary, secondary and exploratory objectives. Upon recovering from surgery (within 28-35 days after surgery), participants will resume single agent intravenous VB-111 every 6 weeks until tumor progression is supported by two consecutive time points of tumor growth (based on RANO criteria) or adverse event requiring discontinuation of study drug. Upon initial evidence of contrast-enhancing progression, and if clinically stable, participants may continue with VB-111 infusions. Bevacizumab or biosimilar may be used as supportive care if clinically indicated. Blood samples will be obtained as pharmacodynamics markers throughout the study. Dose holds and symptomatic management will occur based on preset adverse event determination. DLTs will not be determined. The toxicity evaluation period will begin with registration and extend to 30 days after the last treatment day. Participants will be followed for MRI changes, clinical exam and steroid doses from the registration period until the second progression. After tumor progression is confirmed on the second consecutive MRI, VB-111 will stop and participants will be followed every 3 months for vital status until death.

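### PFS6 alpha is split by plain Bonferroni over three overlapping comparisons; Holm's step-down keeps the same error control with more power, and the contrast in Secondary Objective 1 is given no priority

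*Combined protocol and SAP*

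**What the plan says.** Secondary Objective 1 (section 1.3) concerns PFS6 in participants "treated with VB-111 (Group A and Group B) compared to control (Group C), using RANO criteria". Its hypothesis is also about treated participants as a whole: "We hypothesize that a greater percentage of participants who are treated with VB-111 will not have experienced tumor progression at 6 months after treatment". Neither asks a separate question about A alone or B alone.

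Section 13.4 sets out the analysis: "Group comparisons (Group A vs C; Group B vs C; Group A+B vs C) will be conducted using the exact binomial test with Bonferroni adjustment". The overall level is 5%, one-sided. The section does not write out the Bonferroni divisor, rank the three comparisons, or give a PFS6 alternative or power. It calls the test exact binomial without naming a two-sample version. The paragraph opens with a historical pooled analysis "which documented a PFS6 rate of 10" percent.

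The same section says that "a two-sample T-test with Bonferroni adjustment will be used to compare the increase number of expanded TCR clones" between A+B and C. That is one group contrast, and the plan does not say over what the adjustment runs.

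**The concern.** The three PFS6 comparisons share Group C, and the pooled comparison contains both of the others, so the test statistics are strongly correlated. Plain Bonferroni uses neither that overlap nor the fact that the objective singles out A+B vs C. Each test gets a third of the alpha, whatever the others show. With 30 vs 15 participants, the cut-off then matters a good deal. If 1 of 15 in C is progression-free, A+B needs 10/30 (33%) at 5% but 13/30 (43%) at 1.67%. A real benefit is therefore more likely to go undeclared than it would be under another procedure with the same family-wise guarantee.

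**Working it through.** **Inputs**
- Family of three tests, one-sided 5% (section 13.4). Implied per-test level: 0.05/3 = 0.0167.
- Allocation: "sequentially randomized to one of three groups in a 1:1:1 ratio" (section 5.1), with 15 evaluable per arm (section 5.6), so A+B = 30 and C = 15. PFS6 uses the ITT set (section 13.2), so arms may be slightly larger.
- C = 10%: an assumption, borrowed from the historical rate in section 13.4.
- Two-sample one-sided Fisher test: an assumption.

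The plan gives no PFS6 power, so there is no figure to reproduce. Its only power statement (section 13.3) concerns TIL density.

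**Formulas**
- Fisher p-value for x/n1 vs y/n2: P(X ≥ x), with X hypergeometric given the total x + y.
- Power: sum over all outcomes of the binomial probabilities for A, B and C, counting outcomes in which the procedure rejects.
- Bonferroni: reject each test if p ≤ 0.0167.
- Holm: order the three p-values. Reject the smallest if ≤ 0.05/3 = 0.0167, then the next if ≤ 0.05/2 = 0.025, then the last if ≤ 0.05. Stop at the first failure.
- Pooled first: reject A+B vs C if p ≤ 0.05; only then test A vs C and B vs C by Holm at 5%.

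**Results, exact enumeration, C = 10%**

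| A = B | A vs C: Bonferroni → Holm | A+B vs C: Bonferroni → Holm | A+B vs C tested first at 5% |
|---|---|---|---|
| 40% | 22.6% → 34.9% | 36.0% → 38.5% | 61.1% |
| 50% | 45.0% → 58.9% | 62.5% → 65.8% | 82.3% |

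B vs C has the same figures as A vs C. The chance of at least one rejection is identical under Bonferroni and Holm, because both start at 0.0167. Holm's gain comes from the later steps.

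**How the pooled-first gain varies** (A+B vs C, 1.67% → 5%)
- A+B 20%: 2.8% → 10.3% (7.5 points)
- 25%: 7.5% → 20.8% (13.3)
- 30%: 14.8% → 33.8% (19.0)
- 40%: 36.0% → 61.1% (25.1)
- 50%: 62.5% → 82.3% (about 20)
- 60%: 85.0% → 94.4% (9.4)

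Over A+B of 30–50%, Boschloo's test gives 13–19 points, the unconditional exact Z test 18–24 and mid-p 15–24. With ITT arms of 16–18, Fisher gives 18–23 points for A+B of 30–45%.

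**Cost of pooled first.** If A = 50% and B = C = 10%, the chance of any significant contrast is 45% under Bonferroni or Holm and 33% under pooled first.

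**Null check.** With all rates at 10%, the chance of any rejection is about 0.1% under the Bonferroni plan. A+B vs C alone at 5% rejects 0.55% of the time.

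**The case against.** Bonferroni is valid for overlapping tests, and PFS6 is a secondary endpoint with no power claim. Both points stand: this is a loss of efficiency, not an error in alpha.

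A reader might infer that the plan throws away 20 to 25 points of power for nothing. The documents do not support that. The figure compares a family of three controlled tests with one contrast at the full 5%, and applies only to about 30–50% vs 10% under the assumptions listed. Holm, the change without cost, recovers about 3 of those points. The rest requires ranking the pooled contrast first, and that loses power if only A works. This scenario bears on the study's rationale: "To further explore the role of priming, this study will explore the effects of single-dose neoadjuvant VB-111, followed by adjuvant treatment". The sponsor may reasonably want A vs C to stand on its own.

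A reader might also infer that the Bonferroni wording on the TCR test is empty and should go. But Table 4 schedules TCR blood sampling before neoadjuvant treatment, at surgery, before adjuvant cycle 1 and with every adjuvant MRI, and Hypothesis 3 concerns subsets of clones. The adjustment may cover time points or subsets, so removing it could drop needed control.

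Nor is a missing A vs B comparison of PFS6 a defect. Objective 1 does not ask for it, section 13.6 plans log-rank comparisons of PFS among the three groups, and the primary TIL test already sets A against B+C. An A vs B estimate would be an optional addition.

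Finally, the test might be read as one-sample against a fixed 10%. The cut-off for n = 15 is then 5 successes at 5%, 2.5% and 1.67% alike. For n = 30 it is 7 at 5% and 8 at either smaller level. Holm would gain nothing: the pooled test reaches the 5% step only after both arms have at least 5, which makes at least 10 together. Pooled first would gain 7–17 points for A+B of 20–35%. But the named comparisons are between groups, so the two-sample reading is the natural one.

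**Conclusion.** The concern holds as a point about efficiency and priority. Section 13.4 places the one contrast named in Secondary Objective 1 in an unranked family of three and uses a procedure that Holm dominates. Under a two-sample one-sided Fisher test, divisor 3, 15 per arm and C = 10%, Holm adds 12 to 14 points for each single-arm comparison when A = B = 40–50%, and about 3 points for A+B vs C. It has no downside.

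Giving A+B vs C the full 5% would add 20 to 25 points at those effects, but only 7.5 to 13 at 20–25% vs 10%, where power stays at 10–21% even so. That is a trade-off for the sponsor, not a correction. The size depends on a control rate and an exact test that the plan does not fix for PFS6.

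**What to change.** In section 13.4:

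1. Replace Bonferroni with Holm's step-down procedure for the three PFS6 comparisons at one-sided 5%, and name the two-sample exact test. This changes wording only and has no statistical cost.
2. Decide, and record the reason, whether A+B vs C should lead. If so, test it first at the full one-sided 5%, and test A vs C and B vs C by Holm at 5% only if it is significant. This matches Objective 1 and controls family-wise error at 5%. Its cost is the loss of power when only A works.
3. For the TCR clone test, state which comparisons (time points, clone subsets or other) the Bonferroni adjustment covers. Keep the adjustment until that is settled.

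Section 13 requires a protocol amendment if methods for key secondary hypotheses change after the study has begun. Treatment is unblinded after surgery (section 5.4), so the choice should be fixed before anyone examines PFS6 by group.

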# 2. BACKGROUND

### 2.1 Glioblastoma

Glioblastoma is the most common malignant primary brain tumor in adults [1]. Despite multimodal treatment with surgical resection, radiotherapy, and temozolomide, prognosis remains dismal with median progression-free survival of only 6.9 months and median overall survival of 14.6 months [2]. Following progression, salvage therapies have historically provided nominal benefit, with PFS6 rates under 10% [3-5].

The aggressive behavior of glioblastoma is in part due to its highly angiogenic and vascular nature, as well as its unique immunosuppressive microenvironment.

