# 2.2.2 Preclinical and Clinical Trial Data

Preclinical studies have confirmed the antitumor activity of VB-111 in mouse models of Lewis lung carcinoma [40], mouse models of B16 melanoma [40], and nude rat glioblastoma xenografts [44].

Completed Phase 1 and Phase 2 clinical trials have shown overall survival benefit with VB-111 across multiple tumor types, including recurrent glioblastoma, platinum-resistant ovarian cancer, and radioiodine-refractory thyroid cancer.

A Phase 1 all-comers study in participants with advanced solid tumors demonstrated that VB-111 was safe and well-tolerated up to  $1 \times 10^{13}$  VPs, with maximal tolerated dose not reached [45]. No drug-related serious adverse events were observed. In an exploratory post-hoc analysis, evidence of anti-tumor activity was demonstrated after a single-dose administration, with a dosedependent response in median overall survival across a range of tumor types. Median overall survival in lower dose was 173 days vs not reached in the high-dose  $1 \times 10^{13}$  VPs cohort (p=0.0098). Median follow-up in this cohort was 487 days.

A Phase 2 study in participants with recurrent GBM demonstrated a survival benefit for participants treated with VB-111 monotherapy that was continued upon progression with combination treatment of VB-111 and bevacizumab (VB-111 Primed Combination) compared with participants treated with limited exposure of VB-111 (LE), and compared with literature reports of recurrent glioblastoma (rGBM) participants receiving bevacizumab monotherapy. Median PFS was 83 vs 56 days for the Primed Combination vs LE group (p=0.01; HR 0.46 [95% CI 0.23-0.91]). Median OS was significantly greater in the Primed Combination vs LE group (414 vs 223 days) (hazard ratio 0.51 [95% CI 0.26-0.99]; p=0.043). The historical control, constructed from a meta-analysis of 694 rGBM participants treated with bevacizumab monotherapy across 8 studies, showed a median overall survival (OS) of 32 weeks (224 days), significantly lower than the median OS in the Primed Combination group (p=0.0295). The 12-month OS was 57% in the Primed Combination group vs 24% in the historical control (p=0.03).

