# 2.4.5.3 Efficacy Endpoints

Primary efficacy endpoint will be T lymphocyte (TIL) density, and the secondary efficacy endpoint PFS6 will be measured using RANO criteria. RANO criteria [55] as assessed by the investigator will be used to determine eligibility, make treatment decisions, and determine progression. KPS [Appendix A] as assessed by the investigator will be used to determine clinical progression. OS will be calculated based on time-to-event outcome.

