# **13.6 Exploratory Analyses**

Variables involved in exploratory analyses will be examined graphically and summarized by descriptive statistics. Data transformation may be applied to quantitative variables prior to analyses if deemed necessary.

Bivariate association analyses will be conducted to evaluate the associations between exploratory biomarkers and clinical outcomes and adverse events for the objectives listed in 1.4. The analyses will be performed for each group separately and/or combined as deemed appropriate. Specifically, Pearson or Kendall's tau correlation coefficients will be calculated to evaluate the association between quantitative variables, Chi-squared tests or Fisher's exact tests will be used to examine the association between categorical or ordinal variables, and ANOVA will be performed to study the association between a quantitative variable and a categorical variable. The association between biomarkers and clinical outcomes (PFS and OS) will be evaluated using Cox regression and elastic net regularized regression for variable selection. For markers with multiple measurements over time, data at a specific time point or change from pre-treatment will be used in the above bivariate analyses as deemed appropriate.

Changes in markers pre- and post- treatment will be assessed using paired t-tests.

Between-group comparisons will be conducted for PFS, OS, TIL density, interferon and cell cycle-related genetic signatures, and IHC expression. Survival analyses via Kaplan-Meier curves and log-rank tests will be used to estimate and compare PFS, second PFS, and OS between Group A, Group B, and Group C.

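### Section 13.4 names a one-sample test, with no stated null, for three PFS6 comparisons against concurrent Group C, and the verdict depends on how that is read

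*Combined protocol and SAP*

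**What the plan says.** Secondary Objective 1 (section 1.3) is to estimate PFS6 in participants "treated with VB-111 (Group A and Group B) compared to control (Group C), using RANO criteria". Its hypothesis gives a direction, higher with VB-111, but no null value.

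Section 13.4 first cites a pooled historical PFS6 rate of 10%. It then lists three comparisons, A vs C, B vs C and A+B vs C, which "will be conducted using the exact binomial test with Bonferroni adjustment to compare PFS6 rate at one sided alpha of 5" per cent. It does not say what proportion is tested, whether Group C's rate is treated as known or as estimated, or what part the 10% plays.

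Elsewhere the plan is more specific. Section 13.4 calls its t-tests two-sample, and section 13.6 provides that "Chi-squared tests or Fisher's exact tests will be used to examine the association between categorical or ordinal variables".

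On numbers, section 13.2 assigns PFS6 to the ITT population, and section 5.6 continues recruitment "until 15 evaluable patients in each arm". The ITT arms may therefore exceed 15.

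**The concern.** A one-sample binomial test needs a fixed null proportion. The objective is a comparison with a randomized concurrent arm whose rate is itself estimated from about 15 people. The sentence can be carried out in three ways:

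1. Test each VB-111 group against 10%. Group C then plays no part, and the result supports a claim against history, not over Group C.
2. Test each VB-111 group against Group C's observed rate as though it were known. Group C's sampling error is then ignored.
3. Run a two-sample exact test, which answers the objective. The name in section 13.4 is then wrong, and the choice between Fisher and Boschloo is still open.

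If the choice is left until the data are in, the same counts can be reported as significant or not.

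**Working it through.** The plan gives no sample size, power or critical value for PFS6, so there is no stated figure to reproduce.

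**Inputs.** 15 per arm and 30 for A+B (section 5.6; an assumption for ITT). One-sided level 0.05/3 = 0.0167 for three comparisons, taking the 5% in section 13.4 as the family level, which the text does not settle. Historical rate 10% (section 13.4). Event counts are illustrative, because the documents give no expected PFS6 for VB-111.

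**Critical values against a fixed 10%.**
- n = 15: P(X ≥ 4) = 0.0556 and P(X ≥ 5) = 0.0127, so reject from 5/15.
- n = 30: P(X ≥ 7) = 0.0258 and P(X ≥ 8) = 0.0078, so reject from 8/30.

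**Same data, different readings (one-sided p).** Fisher for 5/15 vs 1/15 is [C(15,5)·C(15,1) + C(15,6)] / C(30,6) = (45,045 + 5,005) / 593,775 = 0.084. Against Group C's rate as fixed, it is P(X ≥ 5 | 15, 1/15) = 0.0022.

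| Data | vs 10% | vs C's rate as fixed | Fisher | Boschloo |
|---|---|---|---|---|
| A 5/15, C 1/15 | 0.0127 | 0.0022 | 0.084 | 0.049 |
| A 5/15, C 2/15 | 0.0127 | 0.0398 | 0.195 | 0.113 |
| A 6/15, C 2/15 | 0.0022 | 0.0096 | 0.107 | 0.057 |
| A+B 9/30, C 2/15 | 0.0020 | 0.0136 | 0.198 | 0.124 |

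At 0.0167, both one-sample readings reject in rows 1, 3 and 4, and neither two-sample test does. In row 2 the one-sample readings disagree with each other. If the 5% were unadjusted, row 2 would still split: 0.0127 and 0.0398 against 0.195 and 0.113. With A and C both at 5/15, the test against 10% still gives 0.0127, while Fisher gives 0.650.

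**Family-wise error for a claim over Group C.** All arms have the same true rate p. The binomial probabilities are summed over every (a, b, c) at which at least one of the three comparisons rejects. For the fixed 10% null this is P(A ≥ 5 or B ≥ 5 or A+B ≥ 8).

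| True p | Null 10% | Null = C's rate, C = 0 may not reject | Null = C's rate, C = 0 may reject | Fisher | Boschloo |
|---|---|---|---|---|---|
| 10% | 2.7% | 4.4% | 24% | 0.1% | 0.6% |
| 12% | 5.7% | 6.8% | 21% | 0.2% | 0.9% |
| 15% | 13% | 9.9% | 19% | 0.4% | 1.4% |
| 20% | 34% | 13% | 16% | 0.8% | 2.0% |

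At 30%, Fisher reaches 1.1% and Boschloo 2.9%.

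With the fixed 10% null, the error passes 5% at a true rate of 11.6% for 15 per arm. For 16, 17, 18, 19 and 20 per arm it does so at 12.7%, 13.3%, 12.5%, 11.8% and 11.2%.

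**How far above 10% could the rate lie?** Section 2.1 describes salvage therapies "with PFS6 rates under 10" per cent. Section 2.2.2 reports that "Median PFS was 83 vs 56 days for the Primed Combination vs LE group". If PFS were exponential, six months (182.6 days) would give 0.5^(182.6/56) = 10% and 0.5^(182.6/83) = 22%.

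**The case against.** The strongest reply is that the sentence describes group comparisons, the objective names Group C, and the hypothesis gives a direction. A null of no higher rate than Group C can be inferred, a test that never uses Group C would contradict the sentence it implements, and the 10% is only said to be available. On that view this is a naming slip. That reading is plausible. But the plan says two-sample and names Fisher's test where it means them, so a programmer could run the one-sample test in good faith.

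Second, the large error rates need true rates that the documents do not state. This stands: at 10% the fixed-null reading is within 5%. So is the observed-rate reading if Group C at 0/15 cannot reject, and that convention is not in the plan either. The phase 2 extrapolation is weak support: both medians come from VB-111-treated groups, the exponential form is assumed, and this trial counts PFS6 from surgery. The change of verdict on identical data needs none of these assumptions.

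Third, PFS6 is secondary and unpowered, the primary analysis is untouched, and section 13.6 already plans exploratory log-rank comparisons of PFS and OS across the arms. This limits the consequence but does not remove the ambiguity.

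**Conclusion.** The concern holds. As named, the test either ignores Group C or treats its observed rate as known, and neither answers Secondary Objective 1. The reading chosen can reverse the verdict on the same counts. At the documents' own 10% rate, the fixed-null reading keeps the family-wise error at 2.7%. It exceeds 5% once the common true rate passes 11.6%, with 15 per arm and 0.05/3 per comparison. The two-sample tests stay at or below 1.1% (Fisher) and 2.9% (Boschloo) for true rates of 10% to 30%. This should be corrected before PFS6 data are analysed, but it does not threaten the trial's main conclusion.

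A side matter, not needed for this conclusion: section 2.4.5.3 says RANO "as assessed by the investigator will be used to determine eligibility, make treatment decisions, and determine progression", and section 5.4 unblinds treatment after surgery, while section 11 also refers to blinded central review. Which read supplies the radiographic part of PFS6 should be reconciled.

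**What to change.** In section 13.4, name a two-sample exact test for A vs C, B vs C and A+B vs C, either Fisher's (already in section 13.6) or Boschloo's. Set it at one-sided 0.05/3, state that 5% is the family level, and report exact confidence intervals for the differences. Keep the one-sample exact binomial test only for the 10% benchmark, with that null written down and the result labelled as a comparison with history.

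This changes SAP wording only and adds no participants or scans. The price is visible low power. For 30% vs 10% at 0.05/3:

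| Test | 15 vs 15 | 30 vs 15 |
|---|---|---|
| Fisher | 8% | 15% |
| Boschloo | 16% | 25% |
| One-sample vs 10% (Group C unused) | 48% | 72% |

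The higher figures in the last row do not measure power for a claim over Group C. The estimates and intervals will carry most of the information.

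On the side matter, state which read supplies the radiographic component of PFS6 and use the other as a sensitivity analysis. Keep clinical deterioration and death as progression events, as section 11.2.4 has them. Blinded central review would limit bias and central review is already planned, but only section 11's opening text calls it blinded. The blinding of the retrospective review in section 11.5 would need to be confirmed.
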